Description		Screening		Test day 1	P/V or V/P	Test day 2	Wash-out period	Test day 3	V/P or P/V
Day		within 14 days before Visit 2		1		4		12-30	Test day 4
Screening									
• Written informed consent, assignment of the subject number									
• Personal, family and medication history									
• Self-assessment mental health and sleeping habits, MADRS-S, EHI									
• Physical examination									
• ECG, Blood sample									
Treatment periods									
• Electronic intake diary									
• Electronic AE diary (VAS headache, gastrointestinal discomfort, dizziness; free text)	3.5 days				x				x
Wash-out period (8-82 days between V3 and V4)	8-82 days						x		
Test days									
Pre-examination test days									
• Vital signs									
• Flu-like symptoms, common cold symptoms									
• Pregnancy test (Visits 2 and 4)									
• Questionnaire drugs and alcohol consumption during last 3 days resp. past 12 hours									
• Sleep duration last 24 hours									
• AE recording									
• VAS headache, gastrointestinal discomfort, dizziness; VAS tiredness, motivation									
Assignment of the randomization number	5 min		x						
Intake of study medication	5 min		x	x	x		x	x	x
Waiting time (incl. continental breakfast 2 hours after intake of study medication)	4 h		x		x		x		x
Before start of testing									
• AE recording									
• VAS headache, gastrointestinal discomfort, dizziness; VAS tiredness, motivation	15 min		x		x		x		x
Testing Phase – part 1									
• n-Back			x		x		x		x
• Processing speed task SDMT	45 min								
• Digit Span									
Break	15 min		x		x		x		x
Testing Phase – part 2									
• BOMAT	15 min		x		x		x		x
rMT measurement using TMS	15 min	x			x				x
Final Examination									
• AE recording									
• VAS headache, gastrointestinal discomfort, dizziness; VAS tiredness, motivation	15-20 min		x		x		x		x

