3.7 Risks / Benefits

Fampridine application

Although a short term application of 10 mg fampridine twice daily in healthy participants is generally well tolerated (March and Cardi 2009), participants will be informed of the possible risks associated with taking fampridine. Specific risks that participants need to be aware of are listed below:

- The most frequently occurring AEs included dizziness, headache, insomnia and gastrointestinal discomfort. No discontinuations due to AEs were reported in a study with healthy subjects after administration of a single 10 mg dose (Smith, Swan et al. 2010) as well as after 5 days of twice daily fampridine SR 10 mg in healthy subjects (March and Cardi 2009).
- Fampridine is excreted primarily unchanged in the urine (Blight and Henney 2009). Tolerability and incidence of AEs appear to be dose related, occurring more frequently at plasma concentrations > 100 ng/mL (Van Diemen, Polman et al. 1993). We will therefore exclude subjects with renal impairment to avoid higher plasma levels. To assess renal impairment, we will perform creatinine and uric acid levels in plasma.

- Fampridine is excreted primarily through the organic cation transporter 2 (OCT 2). OCT 2 inhibitors or substrates (e.g. Cimetidine, Carvedilol, Propranolol and Metformin) may inhibit elimination of fampridine and increase the risk of adverse events. Subjects with concomitant use of these drugs are excluded from participation.
- Fampridine can cause seizures. We will exclude people with a history of seizures and subjects at risk of lowered seizure threshold due to e.g. sleep deprivation or alcohol withdrawal after alcohol abuse.
- Despite the fact that fampridine at therapeutic and supratherapeutic doses is not associated with QT prolongation in healthy subjects (March and Cardi 2009) we will exclude subjects with any clinically significant ECG abnormalities or history of cardiovascular disease.
- Fampridine might cause nausea and dizziness and have an additive effect with alcohol. Participants will be advised to avoid alcohol, illegal substances, and any medication (especially psychoactive) due to possible interactions during the course of the study.
- An increased risk of bacterial and viral infections is described in the prescribing information. In a study with 47 healthy subjects receiving 10 mg twice daily doses of fampridine SR over 5 days no viral or bacterial infections were reported (March and Cardi 2009).

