5 STUDY OUTCOMES

5.1 Primary Outcome

- High-load working memory performance (3-back (d')) as assessed by a letter n-back task) after repeated intake of study medications (visit 3 and 5).

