7.4 Criteria for withdrawal / discontinuation of participants

Participants have the right to withdraw from the study at any time for any reason without being obliged to give reason. There will be a final examination after withdrawal for whatever reason. The investigator also has the right to withdraw participants from the study if it is in the best interest of the participant.

The following reasons result in withdrawal:

- Adverse events challenging the health of the participant if continuing the study
- Adverse events prohibiting cognitive testing or rMT-measurement, e.g.
 - headache, dizziness and nausea more than mild or
 - having slept less than 4 hours during the last night (Visits 3 and 5).
- Participant being ill at ease during rMT measuring
- Intake of psychoactive substances within 3 days before test days (e.g. benzodiazepines, antidepressants, neuroleptics, cannabis)
- Non-Compliance
- Severe protocol violations
- Administrative troubles
- Positive pregnancy test (test day 1 or test day 3)

- Alcohol intake within 12 hours before start of all visits

Withdrawal date and reason will be listed in the participant enrolment log. Safety data will be analyzed for all participants, who received at least one dose of study medication. There will be no anonymization of the data. For information about data handling see chapter 12.3.

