9.2.2 Assessment of secondary outcomes

- High-load working memory performance(see above) after acute intake of study medication.
- Resting motor threshold (rMT) will be measured during screening procedures and after repeated intake with a biphasic magstim Rapid2 stimulator (The MAGSTIM® Company Ltd, Whitland, UK) and a 70 mm figure-of-eight coil.

rMT will be determined by measuring the motor evoked potential (MEP) in the abductor digiti minimi according to (Rossini 2001). rMT will be defined as the lowest stimulation intensity by stimulating the primary motor cortex of the left or right hemisphere required to induce an MEP in the abductor digiti minimi of the dominant hand in at least 5 out of 10 trials. In case of a relaxed target muscle, a positive MEP is defined as an MEP with $\geq 50 \mu\text{V}$ peak-to-peak amplitude (Rossini 2001).

The coil will be held tangentially to the skull over M1, approximately four cm lateral and one cm anterior to the Vertex. Additionally, the coil-handle points backwards at an angle of 45° to the corresponding parasagittal line. Then the coil will be shifted systematically in steps of approximately one cm in anterior, posterior, lateral and medial direction. Stimulation will be performed at an initial output intensity of 30% of maximum stimulator's output (MSO) and will be increased in steps of 10% until a twitch is detected. Thereafter, 10 pulses will be applied. If less than five MEPs are observed, stimulator output intensity will be increased by 5 %. Depending on the result, intensity will be further decreased or again increased by steps of two and then one percent until the lowest stimulator intensity is found. Otherwise stimulator output intensity is first decreased 5% and thereafter increased or decreased by steps of two and then one percent until rMT is found. The participant is always allowed to stop the measuring, if he/she feels ill at ease.

Performance in other working memory-related tasks and other n-back outcomes will be measured both after acute and repeated study medication as follows:

- Reaction time_(for correct 3-back responses).
- Performance in a 0-back task (d' measure controlled) as a measure of attention. We will use parallel versions (different sequences) for the four test days

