11.4.1 Datasets to be analyzed, analysis populations

We will apply a Per-Protocol-Analysis, i.e. the analysis of the primary and secondary outcome measures will be only performed with those participants, who completed all tests and investigations. There will be replacement of Drop-Outs until data of 44 participants are completed. Drop-Outs will be thoroughly described to assess the reason(s) for dropping out.

We will recruit up to 4 subjects more towards the end of the trial to prevent under-recruitment due to Drop-Outs. If more than 44 subjects will complete all tests and investigations their data will also be analyzed.

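### The all-tests completer rule in 11.4.1 can discard valid V3 and V5 3-back scores because of an unrelated missing test, and no second efficacy set is planned

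*Combined protocol and SAP*

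**What the plan says.** Section 11.4.1 calls the analysis per-protocol and defines one set for every efficacy outcome: the "analysis of the primary and secondary outcome measures will be only performed with those participants, who completed all tests and investigations". It repeats the completion condition for any participants beyond 44. Drop-outs are replaced until 44 complete, and their reasons for leaving are to be described.

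The primary outcome in 5.1 is 3-back d' "after repeated intake of study medications (visit 3 and 5"). In the study schedule, n-back comes in the first testing block, BOMAT in the second, and "rMT measurement using TMS" after that, on visits 3 and 5.

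On motor threshold, 9.2.2 states: "The participant is always allowed to stop the measuring, if he/she feels ill at ease". Section 7.4 lists "Participant being ill at ease during rMT measuring" as a reason for withdrawal. As examples of adverse events that prevent cognitive testing or motor-threshold measurement, 7.4 also gives "headache, dizziness and nausea more than mild or" "having slept less than 4 hours during the last night (Visits 3 and 5"). Section 3.7 says of the drug: "The most frequently occurring AEs included dizziness, headache, insomnia and gastrointestinal discomfort".

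The only other analysis set is the safety set (at least one dose, 11.4.5). Section 11.4.7 codes missing data as NA and refers drop-outs back to 11.4.1.

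**The concern.** There are two separate problems.

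**Lost data.** Whether a person completed BOMAT or the motor-threshold measurement has no bearing on whether their 3-back score is valid. Yet the rule removes the person from the primary analysis if either is missing.

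**Selection on tolerability.** Headache, dizziness, nausea and short sleep can lead to withdrawal, and they overlap the commonest listed adverse events of fampridine. Completion may therefore depend partly on tolerating the drug, whereas 4.2 states the objective for healthy young participants in general. Describing why people dropped out does not show whether the estimate changes when they are left out, and no second efficacy set or sensitivity analysis is planned that could show it.

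Both periods of an excluded person leave together. What is at stake is therefore which population the estimate describes, not an imbalance between treatments.

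**Working it through.** **1. The plan's own figure.** Inputs from 11.2: dz = 0.5, two-sided α = 0.05, paired t-test, power 90%. Power is P(|T| > t₀.₉₇₅,ₙ₋₁), where T is noncentral t with n − 1 degrees of freedom and noncentrality dz·√n. At n = 44 the noncentrality is 0.5 × √44 = 3.317 and power is 0.9000. At n = 43 power is 0.8931. So N = 44 reproduces exactly, and since it counts completers, replacement protects it.

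**2. How many results the rule requires.** From the study schedule:
- n-back, SDMT, digit span and BOMAT at visits 2 to 5: 4 × 4 = 16
- motor threshold at visits 3 and 5: 2
- total 18; used by the primary outcome: 2; not used but required: 18 − 2 = 16

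This counts scheduled items. It does not say how often one will be missing, and the documents give no rate.

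**3. When a full 3-back pair is lost.**

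| Event | Both primary scores exist? | Kept under 11.4.1? |
|---|---|---|
| Motor threshold stopped at V5 | Yes | No |
| Single other test missing at V2–V5, no withdrawal | Yes | No |
| Withdrawn at V3, after n-back | No, V3 only | No |
| Withdrawn before n-back at V5 | No, V3 only | No |

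**4. Gain from keeping people with both scores**, added to 44 completers, by the formula in step 1:

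| Pairs | Power | SE relative to 44 |
|---|---|---|
| 44 | 90.0% | 1 |
| 45 | 90.7% | √(44/45) = 0.989 |
| 46 | 91.3% | √(44/46) = 0.978 |
| 48 | 92.4% | √(44/48) = 0.957 |

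The last row is a best case: four extra people, all with both scores, and an SE 4.3% lower.

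**5. Gain from people with a V3 score only.** Assumptions: generalised least squares with treatment and period terms, random intercept, paired-difference SD of 1, 22 completers per sequence, plus four placebo-first people who leave during the fampridine period. Equivalent n = 44 × (SE without them / SE with them)².

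| Assumed within-person correlation | SE reduction | Equivalent n | Power |
|---|---|---|---|
| 0.3 | 1.43% | 45.3 | 90.8% |
| 0.5 | 1.03% | 44.9 | 90.6% |
| 0.7 | 0.62% | 44.6 | 90.4% |

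**6. Why one-score data need a period term.** The model in 11.4 names condition, subject, sex and age, but not period. If those four scores enter a model without period, and practice raises second-period scores by an assumed 0.5 to 1.0 SD of the paired difference, the treatment estimate shifts by 0.006 SD (gain 0.5, correlation 0.7) to 0.029 SD (gain 1.0, correlation 0.3). With the term the shift is 0.

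**7. Illustration of selection, on assumed values only.** Suppose 44 completers average 0.50 and k people withdrawn on fampridine would have had effect v. The overall mean is (44 × 0.50 + k·v)/(44 + k).

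| k | v = 0 | v = −0.5 | v = −1.0 |
|---|---|---|---|
| 2 | 0.478 | 0.457 | 0.435 |
| 4 | 0.458 | 0.417 | 0.375 |

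Nothing in the documents supports any particular k or v.

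**The case against.** **The routes to losing a full pair are few.** Someone withdrawn at V3 never has a V5 score. BOMAT is time-limited and scored by summing correct answers, so running out of time still yields a score. Motor threshold is also measured at screening, and syncope there excludes. This stands: stopping the motor-threshold measurement at V5 is the one concrete route that the protocol itself describes, and the selection is partial, since mild symptoms do not lead to withdrawal.

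**The strict reading may not be intended.** NA coding (11.4.7) and exclusion flags per subject, visit and task (12.3.3) fit better with task-level exclusion than with removing the whole person. It is also unclear whether someone missing one test counts as a drop-out to be replaced. But neither passage overrides the explicit wording of 11.4.1. They show that a task-level set is feasible and that the sections need reconciling.

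**The symptoms are qualified.** Section 7.4 lists them as examples of events that prevent testing, and people who cannot be tested lack scores under any analysis set. True. However, the section names those symptoms at more than mild severity as such events, and an event that prevents only the motor-threshold measurement is enough for withdrawal.

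**A completer set is defensible for a proof-of-concept crossover, and drop-outs are described.** As one analysis among others it is. As the only efficacy analysis it leaves its own influence untestable. Section 11.4.6 permits further analyses if reviewers demand them or other studies find relevant effects or confounders, which does not amount to a planned sensitivity analysis.

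**The remedy cannot cure tolerability selection.** Correct, since assessment after withdrawal covers only adverse events and vital signs (9.4.2). It cures the discarding of valid scores and makes part of the dependence visible.

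**Conclusion.** The concern holds and should be fixed. As written, 11.4.1 makes the primary analysis depend on 16 results that do not enter it, and the plan has no second efficacy set.

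The consequence for precision is small: at best 92.4% power against 90.0%, assuming dz = 0.5 and four extra people with both scores. Planned power is intact, so this is not a criticism of the sample size. The size and direction of any tolerability selection cannot be derived from the documents, and none is claimed. If non-completion is unrelated to the drug–placebo difference, there is no bias. The case rests on valid primary data being dropped for reasons unrelated to the primary outcome, and on a dependence on completion that the planned analyses cannot reveal.

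**What to change.** Replace the single completer set in 11.4.1 with sets defined outcome by outcome.

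- **Primary analysis:** all randomised, dosed participants with valid 3-back d' at V3 and V5, whether or not other tests are complete. Define a valid score before unblinding, for example through the task flags in 12.3.3, and say how non-compliant participants are handled.
- **Sensitivity (a):** participants with at least one of the two scores, in the mixed model with a period term added.
- **Sensitivity (b):** the all-tests completers, as now planned.
- **Table:** withdrawals by treatment at withdrawal and by sequence, with reasons.
- **Wording:** reconcile 11.4.1 with 11.4.7 and 12.3.3, keep the target of 44 completers, and state that none of these sets corrects tolerability selection.
- **Optional:** a missing-not-at-random run over a range of assumed values for those withdrawn on fampridine, labelled illustrative.

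The clinical withdrawal rules are not touched. The cost is SAP wording, one table and two extra model runs, with no extra visits or participants. The limits are that (a) relies on missing-at-random, which is doubtful for people withdrawn for symptoms, and that any missing-not-at-random run rests on assumed values.

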11.4.2 Analysis for the primary outcome

A significance level of $p < 0.05$ will be considered as significant.

The dependent variable is the primary outcome (i.e. 3-back (d')) after repeated administration of study medication). The independent variable of interest is the experimental condition (placebo or verum).

To control for possible confounders or moderators, we will also consider tiredness, motivation, headache, gastrointestinal discomfort, dizziness, mood as assessed by MADRS-S, potassium blood concentration at screening, body weight, duration of washout period and vital signs as covariates (each covariate entering the statistical analysis separately). In case of a significant (i.e. after Bonferroni correction for multiple comparisons) interaction between independent variables of interest and covariates, post-hoc analysis will be applied to describe the interaction effect.

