8 STUDY INTERVENTION

8.1 Identity of Investigational Products

8.1.1 Experimental Intervention

Active study medication consists of 7 tablets of fampridine 10 mg formulated for oral administration taken in the morning and evening 12 h apart without food. Tablets must be administered whole: do not divide, crush, chew, or dissolve Fampyra® retard tablets.

There will be a washout period of at least 8 days equaling over 30 half-lives of the active substance fampridine ($t_{1/2} = 6$ h) between experimental and control intervention and up to 82 days (12 weeks) depending on the individual scheduling of each subject.

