11.2 Determination of Sample Size

We are interested to detect a drug effect with at least medium effect size. The estimation of N=44 is based on a power analysis using dependent two-tailed t-tests assuming to detect a medium effect size (Cohens $dz = 0.5$) with a power of 90% at $\alpha=0.05$ (software: G-power 3).

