11.4 Planned Analyses

All analyses will be performed with the software R. The differences between the experimental conditions (placebo, verum) will be analyzed using linear mixed models in combination with analysis of variance (SS II). Subjects will be included as the random effect of the mixed model. Sex and age will be inserted as covariates.

In case of significant interactions between covariates and experimental condition, post-hoc tests will be applied to describe the interaction.

To control for an influence of other variables, possible confounders will be entered into the model as covariate (each possible confounder entering the statistical analyses separately and corrected for multiple comparisons with the Bonferroni method).

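### The planned washout covariate cannot adjust for, and has almost no power to show, an effect of washout length on the period-2 score; a washout-by-period term beside a period effect would do both

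*Combined protocol and SAP*

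**What the plan says.** The study schedule gives "Wash-out period (8-82 days between V3 and V4". Section 8.1.1 justifies the minimum pharmacologically ("There will be a washout period of at least 8 days equaling over 30 half-lives") and lets the gap run "up to 82 days (12 weeks) depending on the individual scheduling of each subject".

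The primary outcome (section 5.1) is 3-back d' after repeated intake, taken at visit 3 in period 1 and visit 5 in period 2. Section 6.2.1 defines two sequences, placebo-verum and verum-placebo.

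Section 11.4 specifies a linear mixed model with sex and age as covariates: "Subjects will be included as the random effect of the mixed model". In section 11.4.2 the independent variable of interest is condition. A list of possible confounders or moderators follows, and it includes "duration of washout period and vital signs as covariates (each covariate entering the statistical analysis separately". The only interaction provided for is covariate by independent variable of interest, hence washout × condition. Section 11 names no period, visit or sequence term, and no washout × period term. Section 11.4.1 restricts the analysis to participants with complete data, and section 11.4.3 carries the same approach to the secondary outcomes.

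**The concern.** Visit 3 precedes the washout, so washout length can act only on period 2. The half-life argument covers residual drug. It does not cover loss of practice on a task given on four test days. The plan itself names washout as something to control for, so it matters whether the terms it provides can do so.

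They cannot do the confounder part of that job. A main effect of a participant-level covariate leaves the within-participant contrast untouched. The interaction with condition asks whether the drug effect varies with washout, which is a different question. Variance from unequal gaps therefore stays in the error of the primary contrast, and a null washout × condition result could be taken as reassurance that it does not give.

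**Working it through.** **Plan's own figure.** Section 11.2 uses a "power analysis using dependent two-tailed t-tests" for "a medium effect size (Cohens $dz = 0.5$) with a power of 90% at $\alpha=0.05$ (software: G-power 3". The exact noncentral-t calculation first reaches 90% at N = 44 (power 0.9000), so the stated N reproduces.

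**Inputs from the documents.** 44 complete pairs (section 11.4.1: "There will be replacement of Drop-Outs until data of 44 participants are completed"); washout 8 to 82 days, ratio 82/8 = 10.25; minimum washout 8 × 24 / 6 = 32 half-lives.

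**Assumptions, not in the documents.** 22 participants per sequence; washout uniform over 8-82 days and unrelated to sequence; a linear change in the visit 5 score from day 8 to day 82 of 0 to 2 SD, where 1 SD is the residual SD of the verum-placebo difference.

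**Algebra.** Let d = verum minus placebo for one participant, s = +1 for placebo-verum and -1 for verum-placebo, and g(w) the effect of washout w on the period-2 score, with slope β. Then d = δ + s·g(w) + e.

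1. *Main effect.* A washout term with the same value at visits 3 and 5 drops out of d. In one simulated trial the condition estimate and SE were 0.37829 and 0.16379 with and without it.
2. *Washout × condition.* This is the slope of d on w, with expectation β(n_PV − n_VP)/N. It is zero at 22/22. At 24/20 it is 4/44, about 9% of β.
3. *Washout × period.* This is the slope on s·w, with expectation β.
4. *Different slopes by sequence.* With equal sequences, washout × condition estimates (β_PV − β_VP)/2 and washout × period estimates (β_PV + β_VP)/2. A carry-over confined to verum-first therefore appears at half size in each. For a true slope of -1 there, simulation gave 0.505 and -0.502.

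**Precision.** A uniform spread adds b²/12 to the variance of d for a loss of b SD. With a period term only, SE ≈ √((1 + b²/12)/44), which gives 0.157 at b = 1.0 and 0.164 at b = 1.5. Simulation (4,000 to 6,000 trials per row) agrees:

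| Assumed loss (SD) | Washout × condition significant | Washout × period significant | SE, period only | SE, period + washout × period |
|---|---|---|---|---|
| 0 | 5% | 5% | 0.150 | 0.152 |
| 0.5 | 5% | 15% | 0.151 | 0.152 |
| 1.0 | 4% | 45% | 0.156 | 0.152 |
| 1.5 | 5% | 77% | 0.163 | 0.152 |
| 2.0 | 4% | 95% | 0.174 | 0.152 |

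At dz = 0.5, power with a period term alone is 89.5%, 88.0% and 80.6% for losses of 0.5, 1.0 and 2.0 SD. With washout × period added it is 89.4% throughout. The mean drug estimate was 0.50 for a true 0.50 in every scenario.

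**Why both SE columns contain period.** The SE of the planned model, which has no period term, also depends on the mean period effect. With an assumed offset of 0.3 SD at day 8 it is 0.159 at a 1.0 SD loss and 0.177 at 1.5 SD. At 1.5 SD, 0.014 of the total drop of 0.025 (0.177 to 0.163 to 0.152) then comes from the period term alone. Only the remaining 0.011 belongs to the washout term.

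**The case against.** Several points on the other side stand.

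- *No bias.* A reader might infer that the drug estimate is biased or the primary test invalid. Neither follows. With randomised, balanced sequences and washout unrelated to sequence the estimate is unbiased, and simulated type I error was at or below 5%. A chance difference in gap length between sequences is part of the same variance, not a second harm.
- *The moderator test is legitimate.* The list covers moderators as well as confounders. Washout × condition validly asks whether the drug effect depends on washout, and it catches half of a verum-first carry-over. A reader might infer that the plan would report a null result as showing no influence of washout; the documents do not say so.
- *Losses of 1.0 SD or more have no support in the documents.* Only one gap is long, from visit 3 to visit 4. The visit 4 session repeats the battery between that gap and the primary visit 5 score, and parallel versions are used on every test day.
- *Long gaps may be uncommon.* The schedule places test day 3 on days 12-30. With visit 3 on day 4 that is a washout of 8-26 days, and section 9.4.1 requires repeat screening beyond 26 days. If 80% of washouts fell within 8-26 days (an assumption), the gain at a 1.0 SD loss would shrink to 0.154 against 0.152, and washout × period would be significant in about 30% of trials. If all fell there, there would be no gain.

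None of this makes either planned form able to adjust for a common effect of washout on visit 5.

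**Conclusion.** The point holds as a fault of model form, modest in size. Duration of washout is listed for control, but its main effect cannot change the drug contrast in complete pairs, and washout × condition has essentially no power against a common period-2 effect when sequences are balanced. The first statement needs only complete pairs and a random subject effect; the second needs near-equal sequences among completers.

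The cost is lost precision and an uninformative check, not systematic bias. The precision loss is visible only for assumed losses of about 1 SD or more over a wide spread of washouts. Both the loss and the spread are assumptions.

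**What to change.** In section 11.4.2:

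1. Include period as a fixed effect.
2. For the washout covariate, enter centred washout duration × period, with the washout main effect carried alongside, as the confounder adjustment.
3. Keep washout × condition as a moderator analysis only, and state that a null result is not evidence that washout had no influence.
4. Report the washout slope in each sequence descriptively, because neither interaction alone separates practice loss from carry-over. Washout is not randomised, so these slopes are observational.

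The sponsor should also reconcile the day range for test day 3 with the 8-82 day washout.

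All data are already collected. The adjustment uses one degree of freedom beyond period and widens the SE by about 1% if washout has no effect (0.150 to 0.152).
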